#### 3.2 Selection of Patients

The total number of patients to be enrolled on this study is 58 subjects for 53 evaluable patients.

#### 3.2.1 Inclusion Criteria

Each patient must meet all of the following inclusion criteria to be enrolled in the study:

- Voluntary written informed consent before performance of any study-related procedure not part of normal medical care, with the understanding that consent may be withdrawn by the subject at any time without prejudice to future medical care.
- Female subject is either:
  - o post-menopausal for at least one year before the screening visit, or
  - o surgically sterilized, or
  - willing to use an acceptable method of birth control (ie, a hormonal contraceptive, intra-uterine device, diaphragm with spermicide, condom with spermicide, or abstinence) for the duration of the study and at least 1 month after the last dose of alisertib.
- Male subject, even if surgically sterilized (ie, status postvasectomy), agrees to use an acceptable barrier method for contraception (condom with a spermicidal agent), or completely abstain from heterosexual intercourse during the entire study treatment period through 4 months after the last dose of alisertib.
- Absolute neutrophil count (ANC) > 1500/mm³, platelets > 100,000/mm³, Hgb > 9 g/dL. Total bilirubin ≤ 1.5 x upper limit of nomal (ULN), SGOT (AST) and SGPT (ALT) < 2.5 x ULN. AST and/or ALT may be up to 5X ULN if with known liver mets

- Adequate renal function as defined by: Calculated creatinine clearance must be ≥ 30 mL/minute(see Cockcroft-Gault formula in Section 9.5)
- Eastern Cooperative Oncology Group (ECOG) performance status 0-2 (refer to Section 9.4)
- Pathologic diagnosis of malignant mesothelioma (any primary site is acceptable)
- Have unresectable malignant mesothelioma (any histology)
- Received at least one prior pemetrexed-based chemotherapy for unresectable disease, unless within 3 months of receiving platinum-pemetrexed therapy for neoadjuvant or adjuvant treatment that has been unsuccessful.

- Up to 4 prior lines of systemic therapy (biologic or chemotherapy) are allowed. Maintenance therapy after 4-6 cycles of front-line chemotherapy is still considered 1 line of therapy and is not considered 2 separate therapies.
- Patients must have measurable disease by modified RECIST or RECIST.
   Examinations for assessment of measurable disease must have been completed within 28 days prior to registration.
- Patient must be >/= 18 years of age

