#### 1. INTRODUCTION AND STUDY RATIONALE

#### 1.1 Overview of the Disease

Unresectable malignant mesothelioma is a challenging disease that has typically had poor responses to chemotherapy. Response rates to systemic chemotherapy have ranged from 3% to 30%.[3] In the front-line setting, the Evaluation of Mesothelioma in a Phase III study of Pemetrexed with Cisplatin randomized 456 patients to single agent cisplatin or the combination of cisplatin and pemetrexed. This study reported improvement in median overall survival (12.1 months vs. 9.3 months; p=0.02).[4] There are currently no Food and Drug Administration (FDA) approved agents in the salvage setting for mesothelioma. Novel agents for refractory patients are desperately needed to improve the therapeutic landscape.

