#### 3.2.2 Exclusion Criteria

Patients meeting any of the following exclusion criteria are not to be enrolled in the study.

- Radiation therapy to more than 25% of the bone marrow. Whole pelvic radiation is considered to be over 25%.
- Prior allogeneic bone marrow or organ transplantation
- Known GI disease or GI procedures that could interfere with the oral absorption
  or tolerance of alisertib. Examples include, but are not limited to partial
  gastrectomy, history of small intestine surgery with significant removel of the
  small intestine, and celiac disease
- Known history of *uncontrolled* sleep apnea syndrome and other conditions that
  could result in excessive daytime sleepiness, such as severe chronic obstructive
  pulmonary disease. Patients who use CPAP or BIPAP at night and have
  controlled sleep apnea syndrome are allowed.
- Requirement for constant administration of proton pump inhibitor, H2 antagonist, or pancreatic enzymes. Intermittent uses of antacids or H2 antagonists are allowed as described in Section 3.4.
- Systemic infection requiring IV antibiotic therapy within 14 days preceding the first dose of study drug, or other severe infection.
- Myocardial infarction within 6 months prior to enrollment or has New York Heart Association (NYHA) Class III or IV heart failure (see Section 9.3), uncontrolled angina, severe uncontrolled ventricular arrhythmias, or electrocardiographic

evidence of acute ischemia or active conduction system abnormalities. Prior to study entry, any ECG abnormality at Screening has to be documented by the investigator as not medically relevant.

- Female subject who is pregnant or breast-feeding. Confirmation that the subject is not pregnant must be established by a negative serum Beta-human chorionic gonadotropin (Beta-hCG) pregnancy test result obtained during screening.
   Pregnancy testing is not required for post-menopausal or surgically sterilized women.
- Patient has received other investigational drugs with 14 days before enrollment
- Serious medical or psychiatric illness likely to interfere with participation in this clinical study.

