### 5. STATISTICAL PROCEDURES

## 5.1 Study Design and Overview of Primary and Secondary Endpoints

The primary objective of this study is to:

• Assess 4-month disease control rate (DCR) in pre-treated patients with unresectable MPM treated with alisertib

The secondary objectives of this study are to:

- To assess the response rate (confirmed and unconfirmed complete + partial responses)
- To assess the progression-free survival.
- To assess overall survival.
- To evaluate the side effects and toxicities associated with this treatment regimen.
- To collect archival tissue, blood, pleural effusion and plasma for correlative studies.

The primary endpoint is the disease control rate at 4 months in patients with unresectable malignant pleural mesothelioma (MPM) treated with alisertib. The trial will be conducted by the Simon's minimax two-stage design and the disease control rate at 4 months will be estimated accordingly (Simon, 1989)

It is assumed that the new regimen will have a target disease control rate of 50% at 4 months. A disease control rate of 30% or lower is considered a failure and the new regimen will be rejected under this circumstance. When the probability of accepting a "bad" regimen (i.e. disease control rate<=30%) is 0.05 and the probability of rejecting a "good" regimen (i.e. disease control rate >=50%) is 0.10, Simon's minimax design requires to enter 24 patients in the first stage. If 7 or less patients are free of disease progression to the treatment at 4 months, the trial will be stopped and the regimen will be declared as ineffective. If there are 8 or more patients are alive and progression-free at 4 months, 29 more patients will be entered in the study to reach a total of 53 patients. By the end of the study, the new regimen will be rejected if disease control rate is less than or equal to 21/53 and will be accepted otherwise. The operating characteristics of the trial are given as follows. When the true disease control rate is 0.30 the probability of stopping the trial early is 57%. On the other

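### On the main eligibility route nothing requires progression after the last therapy, so stable disease carried over from earlier treatment can count as alisertib disease control

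*Combined protocol and SAP*

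**What the plan says.** Section 3.2.1 states the prior-treatment condition for unresectable disease as "Received at least one prior pemetrexed-based chemotherapy for unresectable disease". The same criterion makes an exception for patients within 3 months of platinum-pemetrexed given as neoadjuvant or adjuvant treatment, and there the treatment must have been unsuccessful. Those 3 months are a maximum time since therapy, not a washout. Up to four prior lines are allowed, and maintenance after front-line chemotherapy counts within the first line. Disease must be measurable on an examination within 28 days before registration. The Patient Population paragraph of the Protocol Summary likewise asks only that earlier chemotherapy was received.

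Among the exclusions in section 3.2.2, the one interval for anticancer agents is "Patient has received other investigational drugs with 14 days before enrollment". Radiotherapy is limited by the extent of marrow treated, not by time. Section 3.4 bars other antineoplastic therapy during the study but sets no interval before it.

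The title describes a salvage trial, and section 1.1 argues that "Novel agents for refractory patients are desperately needed to improve the therapeutic landscape".

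Section 5.1 sets the benchmark: "A disease control rate of 30% or lower is considered a failure and the new regimen will be rejected under this circumstance". The target is 50%. At stage 1, "If 7 or less patients are free of disease progression to the treatment at 4 months, the trial will be stopped". The final rule rejects the regimen at 21 or fewer of 53. Section 5.4 defines stable disease as whatever is not response or progression.

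**The concern.** With no control arm, disease control can be credited to the drug only if the patients would otherwise mostly have been progressing. Requiring progression at entry is the usual way to secure that. Here, a patient whose disease was stable on completing front-line chemotherapy or maintenance can satisfy the prior-therapy and measurable-disease criteria. If that patient remains stable at 4 months, whether from the earlier treatment or from indolent disease, the result is a success for alisertib.

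The baseline scan need not follow the last dose of prior therapy, so a late effect of that therapy can also enter the measured change from baseline.

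At stake are both decision rules. A higher rate under an inactive drug makes stopping at stage 1 less likely and acceptance at the end more likely. The words salvage and refractory suggest that the intended population was progressing, but they describe the trial and are not criteria.

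**Working it through.** **Inputs.** From section 5.1: failure rate 0.30, target 0.50, error limits 0.05 and 0.10, stage 1 of 24 patients with stopping at 7 or fewer, stage 2 of 29 more, and rejection at 21 or fewer of 53. Passing stage 1 therefore needs at least 8 of 24, and acceptance at least 22 of 53.

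**Formulas.** For a true 4-month rate p:

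- P(early stop) = P(X1 ≤ 7), with X1 ~ Bin(24, p)
- P(accept) = Σ over x1 = 8 to 24 of P(X1 = x1) × P(X2 ≥ 22 − x1), with X2 ~ Bin(29, p)
- Expected N = 24 + 29 × [1 − P(early stop)]

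**The plan's own figures reproduce.**

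| p | P(early stop) | P(accept) | Expected N |
|---|---|---|---|
| 0.30 | 0.565 (stated 57%) | 0.0466 (limit 0.05) | 36.6 (stated 36.6) |
| 0.50 | 0.032 (stated 3%) | 0.9017 (target 0.90) | 52.1 (stated 52.1) |

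A search for the smallest maximum sample size meeting both error limits also returns 7/24 and 21/53. The design arithmetic is correct.

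**What the 0.0466 depends on.** It is the probability of accepting an inactive drug only if such a drug gives 0.30 in the patients actually admitted. Let f be the share of entrants not progressing at entry and q their 4-month rate without any drug effect, with the other entrants at 0.30:

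p = 0.30 × (1 − f) + q × f

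The documents give neither f nor q. The values below are assumptions chosen only to show sensitivity.

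| f | q | p | P(early stop) | P(accept) |
|---|---|---|---|---|
| 0 | – | 0.30 | 0.565 | 0.047 |
| 10% | 0.50 | 0.27 + 0.05 = 0.32 | 0.479 | 0.087 |
| 10% | 0.60 | 0.27 + 0.06 = 0.33 | 0.438 | 0.115 |
| 20% | 0.60 | 0.24 + 0.12 = 0.36 | 0.320 | 0.231 |

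A rise of two percentage points in the inactive-drug rate nearly doubles the probability of false acceptance (0.087 / 0.047 ≈ 1.9).

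**Cost side.** Section 5.2 expects 1–2 patients per month, so 53 patients take 53/2 = 26.5 to 53/1 = 53 months. If 30% of candidates were no longer eligible, this becomes 26.5/0.7 ≈ 38 to 53/0.7 ≈ 76 months. The stated study duration is 3.2 years, about 38 months.

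**The case against.** The strongest objection is that the benchmark may already fit the population. Section 5.1 presents 30% only as the rate at or below which the regimen fails. It cites no source and does not say that the figure describes progressing patients. The objectives speak of pre-treated patients, and 30% may allow for mixed status at entry. This stands. A reader might infer that the true type I error exceeds 0.05, but the documents do not support that. They show that 30% is not justified for the admitted population, not that it is wrong for it.

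The illustration is also one-sided. It holds all other entrants at 0.30, although 3.2.1 admits performance status 2 and up to four prior lines, for which no rates are given. This too stands, and it is why the figures show sensitivity and do not estimate bias.

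Two further readings go too far. One is that prior failure is never required, but the neoadjuvant/adjuvant exception requires it. The other is that a patient could enter freely within days of chemotherapy. The blood-count thresholds in 3.2.1, and the 14-day exclusion for growth factors and platelet transfusion in 3.2.2, would hold back some recently treated patients. They do not test disease status, so the gap remains.

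Investigators may in practice enrol mainly progressing patients. If so, the added criterion costs little. The written rule still does not ensure it.

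**Conclusion.** The omission is certain from the text: on the unresectable-disease route, neither progression nor any interval from standard chemotherapy or radiotherapy is required. Followed as written, the criteria admit patients whose stability predates alisertib, and such patients can count toward the 8 of 24 and 22 of 53 needed.

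The effect on the conclusion is a risk and has not been shown. Its size rests on two unknowns, the share of non-progressing entrants and their 4-month rate, and on what population the 30% describes. The acceptance probabilities of 0.087, 0.115 and 0.231 are conditional on assumed inactive-drug rates of 0.32, 0.33 and 0.36. The sample size and decision rules are correctly computed and need no change. This is an inexpensive improvement that the trial should make.

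**What to change.** 1. Add to 3.2.1: *Documented disease progression during or after the most recent systemic therapy.* Require the baseline scan to postdate the last prior anticancer therapy, and record the date of progression on the last line.
2. Keep the 7/24 and 21/53 rules, applied to all evaluable patients, as the governing analysis. An amendment partway through could leave the two stages with different entry populations, so which analysis decides should be stated in advance.
3. For patients already entered, pre-specify in section 5.4 a sensitivity analysis of the 4-month disease control rate that excludes those without documented progression at entry, and state whether the conclusion changes.
4. State the source and reference population of the 30% failure rate.
5. Reconcile the 14-day interval for investigational drugs with the absence of any interval for standard chemotherapy or radiotherapy. No length is proposed here.

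The cost is one eligibility line, a scan-timing condition, one date field and one extra analysis. Accrual slows in proportion to the share of candidates who are not progressing. That is minor if few would have been enrolled, but material at 1–2 patients per month if the share were near 30%.

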#### 3.2.2 Exclusion Criteria

Patients meeting any of the following exclusion criteria are not to be enrolled in the study.

- Radiation therapy to more than 25% of the bone marrow. Whole pelvic radiation is considered to be over 25%.
- Prior allogeneic bone marrow or organ transplantation
- Known GI disease or GI procedures that could interfere with the oral absorption
  or tolerance of alisertib. Examples include, but are not limited to partial
  gastrectomy, history of small intestine surgery with significant removel of the
  small intestine, and celiac disease
- Known history of *uncontrolled* sleep apnea syndrome and other conditions that
  could result in excessive daytime sleepiness, such as severe chronic obstructive
  pulmonary disease. Patients who use CPAP or BIPAP at night and have
  controlled sleep apnea syndrome are allowed.
- Requirement for constant administration of proton pump inhibitor, H2 antagonist, or pancreatic enzymes. Intermittent uses of antacids or H2 antagonists are allowed as described in Section 3.4.
- Systemic infection requiring IV antibiotic therapy within 14 days preceding the first dose of study drug, or other severe infection.
- Myocardial infarction within 6 months prior to enrollment or has New York Heart Association (NYHA) Class III or IV heart failure (see Section 9.3), uncontrolled angina, severe uncontrolled ventricular arrhythmias, or electrocardiographic

evidence of acute ischemia or active conduction system abnormalities. Prior to study entry, any ECG abnormality at Screening has to be documented by the investigator as not medically relevant.

- Female subject who is pregnant or breast-feeding. Confirmation that the subject is not pregnant must be established by a negative serum Beta-human chorionic gonadotropin (Beta-hCG) pregnancy test result obtained during screening.
   Pregnancy testing is not required for post-menopausal or surgically sterilized women.
- Patient has received other investigational drugs with 14 days before enrollment
- Serious medical or psychiatric illness likely to interfere with participation in this clinical study.
- Other severe acute or chronic medical or psychiatric condition, including uncontrolled diabetes, malabsorption, resection of the pancreas or upper small bowel, requirement for pancreatic enzymes, any condition that would modify small bowel absorption of oral medications, or laboratory abnormality that may increase the risk associated with study participation or investigational product administration or may interfere with the interpretation of study results and, in the judgment of the investigator, would make the patient inappropriate for enrollment in this study.
- Diagnosed or treated for another malignancy within 3 years of enrollment, with the exception of complete resection of basal cell carcinoma or squamous cell carcinoma of the skin, an in situ malignancy, or low-risk prostate cancer after curative therapy.
- Treatment with clinically significant enzyme inducers, such as the enzyme-inducing antiepileptic drugs phenytoin, carbamazepine or phenobarbital, or rifampin, rifabutin, rifapentine or St. John's wort within 14 days prior to the first dose of alisertib and during the study.
- Known history of human immunodeficiency virus (HIV) infection, hepatitis B, or hepatitis C. Testing is not required in the absence of clinical findings or suspicion. For guidance in defining active infection for hepatitis B, please refer to the WHO guidelines. (World Health Organization, Global Alert and Response

(GAR), Hepatitis B. who.int/csr/disease/hepatitis/whocdscsrlyo20022/en/index4.html)

- Prior administration of an Aurora A kinase-targeted agent, including alisertib
- Receipt of corticosteroids within 7 days prior to the first dose of study treatment, unless patient has been taking a continuous dose of no more than 15 mg/day of prednisone for at least 1 month prior to first dose of study treatment. Low dose steroid use for the control of nausea and vomiting will be allowed. Topical steroid use is permitted. Inhaled steroids are permitted.
- Inability to swallow oral medication or inability or unwillingness to comply with the administration requirements related to alisertib.
- Administration of myeloid growth factors or platelet transfusion within 14 days prior to the first dose of study treatment.
- Persons who are incarcerated at time of enrollment (e.g., prisoners) or likely to become incarcerated during the study.

#### 3.3 Study Treatments

Alisertib drug product is supplied as the ECT dosage form in 10 mg strength, with dose strength expressed as the milligrams of active drug (free acid). The key formulation excipients of the alisertib tablet formulation that aid in the in vivo absorption of the drug are the buffer (sodium bicarbonate), the surfactant (sodium lauryl sulfate), and the enteric coating.

### 3.3.1 Preparation, Handling, and Storage of Drugs

Alisertib ECT are packaged in a 60-cc high-density polyethylene (HDPE) bottle with a rayon coil, induction seal, desiccant packs, and a polypropylene child-resistant cap.

Alisertib is an anticancer drug, and as with other potentially toxic compounds, caution should be exercised when handling MLN8237.

#### **Drug Administration and Dosage Schedule**

The alisertib dose employed in this study will be 50 mg po BID (enteric coated tablet ECT) for 7 days then a 2 week treatment free period for a 21-day cycle. This phase II dosing was established from phase I studies detailed in Section 1.3.

Patients will be instructed to take each oral dose of alisertib with 8 ounces (1 cup, 240 mL) of water. For BID dosing, the doses must be taken at least 6 hours apart.

Patients will be treated until disease progression by modified RECIST or RECIST criteria, withdrawal of consent, or unacceptable side effects.

#### **Alisertib Administration**

Alisertib will be given PO in a dosage of 50 mg BID for 7 Days (Days 1-7) of each 21-day treatment cycle.

Alisertib will be supplied as 10 mg ECT, with the dose strength expressed as milligrams of active drug (free acid). All tablets are to be ingested whole; patients who have difficulty swallowing tablets will be excluded from the study. Antiemetogenic agents may be administered at the discretion of the investigator.

Neutralizing antacids and calcium-containing supplements cannot be taken from 2 hours prior to alisertib dosing until up to 2 hours after dosing

Although not prohibited, the use of benzodiazepines for the prophylaxis or treatment of nausea or vomiting is discouraged because of the potential benzodiazepine-like effects of alisertib.

Study drug will be administered only to eligible patients under the supervision of the investigator or identified subinvestigator(s).

#### Accountability and Mechanism of Drug Destruction

The principal investigator and/or the designated study personnel is responsible for maintaining accurate dispensing records of the study drug. All study drugs must be accounted for, including study drug accidentally or deliberately destroyed. All discrepancies between amounts of study drug dispensed and amounts returned must be documented. Accountability records will include dates, quantities, lot numbers, expiration dates and patient numbers. Under no circumstances will the site principal investigator allow the investigational drug to be used other than as directed by the protocol without prior Millennium approval. If appropriate, drug storage, drug dispensing, and drug accountability may be delegated to the pharmacy section of the investigative site.

Documentation indicating study drug was destroyed will be sent to Millennium.

#### 3.3.2 Dose Modification and Delay

Toxicity will be evaluated according to the National Cancer Institute Common Terminology Criteria for Adverse Events (NCI CTCAE), Version 4.03, effective 14 June 2010 (16). These criteria are provided in the Study Manual and are available online at http://ctep.cancer.gov/protocolDevelopment/electronic applications/ctc.htm

To manage excessive toxicity, reduction of the total alisertib dose can be done by reducing the daily dose administered and/or by interruption of the schedule treatment within a cycle.

